4.5.2 Administration of Abatacept or Placebo

The Central Randomization System will confirm the subject's body weight and age and assign the number of vials of abatacept to allocate for the visit. Subjects will receive doses of study medication at every treatment period visit (Days 1, 15, 29, 57 and 85 during Double Blind Period).

Subjects who are randomized to receive placebo will be given either Dextrose 5% in Water (D5W) or Normal Saline (NS) at the discretion of the investigator. Placebo (NS or D5W) will be supplied by the investigative site.

A ± 3 day window is allowed for the dose on Day 15, a -3 and +7 day window is allowed for the dose on Day 29 and a ± 7 day window is allowed for doses thereafter. Infusions should occur at approximately the same time of day throughout the duration of the study.

All doses of study medication will be administered intravenously in a fixed volume of 100 ml at a constant rate of flow over approximately 30 minutes. Please flush with D5W or NS at the end of the infusion to ensure that the administration line used to deliver the drug solution is adequately cleared; please refer to the infusion set's manufacturer's materials to determine the appropriate flush volume needed to assure delivery of the entire dosage. The infusion solution must be prepared by a qualified staff member and supplied to personnel administering the dose in a container not identifying the contents so as to maintain the blind. The infusion of the fully diluted abatacept/placebo must be completed within 24 hours of reconstitution of the vials. The fully diluted abatacept/placebo may be stored at room temperature or refrigerated at 2°C to 8°C (36°F to 46°F) before use. The fully diluted solution should be discarded if not administered within 24 hours.

All intravenous infusions will be with the subject in the seated position. No adjustments will be made in treatment dose level or schedule. Subjects will be observed for adverse events and vital signs (seated blood pressure, heart rate, and temperature) from the start of each infusion (pre-dose and 60 minutes). There is a ± 5 -minute window for vital sign collection. Subjects will be observed for a minimum of 1 hour from the start of the infusion. The observation period should be extended if clinically indicated.

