4.5.4.2 Dose Modifications Due to an Adverse Event

If there is evidence of toxicity in abnormal laboratory tests or clinical adverse events that, in the judgment of the Investigator, could place the subject at increased risk, study drug administration should be interrupted and the investigator should notify BMS. Subjects may be considered eligible to receive further study medication treatment only if full resolution of the adverse event is documented. Under no circumstances should the dose of study drug be altered due to an adverse event.

The IV infusion dosing window may be extended if the delay is due to an adverse event and if the adverse event has completely resolved. For Day 15, the dose may be delayed up to 7 days. For all subsequent IV infusions, the dose may be delayed up to 14 days. If the adverse event has not resolved within these windows, the IV infusion scheduled for that visit should be skipped (missed one IV dose). For example, if the Day 57 dose could not be administered until the 73rd day, the Day 57 dose should be skipped and the subject's next dose would occur at the Day 85 visit. Only two missed doses are allowed in the Double Blind Period.

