6 STUDY PERIODS, TREATMENT REGIMENS AND POPULATIONS FOR ANALYSES

6.1 Study Periods

In this study, there are four study periods: screening period, double-blind period (DB), open label extension period (OLE), and follow-up period.

The following analysis periods defined below are for analysis purposes. The definitions below indicate the data to be included in the analysis of each specified period. Subjects discontinued during a specified period (DB or OLE) will be considered on-treatment for 56 and 42 days after the last dosing in that period for safety and efficacy analysis respectively. Follow-up period data will be included in one of the analysis periods depending on the time of completing the study.

Screening Period: Starts with the day of enrolment and ends prior or on the day of first dose of study medication (abatacept or placebo).

Double-Blind Period: Starts with the first dosing of double-blind study medication and ends 56/42 days (for safety/efficacy analysis) after the last dose of the double-blind period or the first dosing of OLE, whichever is earlier.

For subjects who completed Period 1 and entered Period 2 prior to Protocol Amendment 2, includes data from first dose date in Period 1 up to the first dose in Period 2.

Open Label Extension Period (OLE): Starts with the first dosing in the OLE and ends 56/42 (for safety/efficacy analysis) days after the last dose in the OLE.

Cumulative Abatacept Safety Period: Starts at the time of the first dose of abatacept (either in the double-blind period for the subjects randomized to abatacept or in the OLE for the subjects randomized to placebo) and continues up to 56 days post last dose of abatacept for safety (AE and laboratory summaries). The last abatacept dose can be last dose in double-blind period for subjects not treated in the OLE.

For subjects who completed Period 1 and entered Period 2 prior to the protocol revision:

- For subjects on abatacept during Period 1:
 - For subjects who do not enter OLE period: starts with the first dosing of Period 1 and ends 56 days after the last dosing of Period 1.
 - For subjects who enter OLE period: starts with the first dosing of Period 1 and ends 56 days after the last dosing of Period 1 combined with OLE period that starts with the first dosing in the OLE period and ends 56 days after the last dosing in the OLE period.
- For subjects on placebo during Period 1:

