- Subjects who completed Period 1 and entered Period 2 prior to the protocol revision:
 - For subjects on abatacept during Period 1 and entering OLE period, it is the sum of the following:
 - ◆ Exposure in Period 1 = (date of first study medication in Period 2 - date of first study medication in Period 1 + 1) + 56.
 - ◆ Exposure in OLE = (date of last study medication in OLE - date of first study medication in OLE + 1) + 56.
 - For subjects on abatacept during Period 2, it is the sum of the following:
 - ◆ Exposure in Period 2 = (date of first study medication in OLE period - date of first study medication in Period 2) - adjustment. Adjustment is the period after 56 days from last study medication from Period 2 to the first study medication in OLE.
 - ◆ Exposure in OLE = (date of last study medication in OLE - date of first study medication in OLE + 1) + 56.
 - For subjects on abatacept during Period 2 and not entering OLE:
 - ◆ Exposure in Period 2 = (date of last study medication in Period 2 - date of first study medication in Period 2 + 1) + 56.

The offset of 56 days is the length of 2 regular dosing cycles and represents approximately 4 times the half-life of abatacept in humans.

Summaries of exposure to study drug will show the distribution of the number of infusions and days on drug, together with the means, standard deviations, medians, minima and maxima, by treatment group.

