Day 141	141	135 - 155		
Day 169	169	156 - 183-	142 - 183	
Day 197	197	184 - 211	184 - 211	
Day 225*	225	212 - 239	212 - 239	
OLE period				
Day 253	253	240 - 267		
Day 281	281	268 - 295		
Day 309	309	296 - 323		
Day 337	337	324 - 351		
Day 365	365	352 - 379		
Day 393	393	380 - 407		

* Day 113 assessment for subjects continuing in Period 2, the upper inclusive limit of this window is the first infusion in Period 2 or 42 days after last dose in Period 1, whichever comes earlier. Day 113 assessment extends 42 days after last dose in Period 1 for subjects discontinuing during Period 1. Similarly, Day 225 assessment for subjects continuing in OLE, the upper inclusive limit of this window is the first infusion in OLE or 42 days after last dose in Period 2, whichever comes earlier. Assessments within 42 days after last dose in Period 2 are included for subjects discontinuing during Period 2.

Table 8.6-3: Day Ranges for Laboratory Assessments at Every Scheduled Visit During the Double-Blind Period and OLE Period

Visit	Target Day	Chemistry	CBC	Total Cholesterol and Triglycerides, fasting
Double-blind period				
Screening	< 1	< 1	< 1	< 1
Day 1 (Baseline)	1	1	1	1

Table 8.6-3: Day Ranges for Laboratory Assessments at Every Scheduled Visit During the Double-Blind Period and OLE Period

Visit	Target Day	Chemistry	CBC	Total Cholesterol and Triglycerides, fasting
Day 15	15	8 - 22		
Day 29	29	23 - 43	15 - 57	
Day 57	57	44 - 71		28 - 56
Day 85	85	72 - 99	58 - 99	
Day 113*	113	100 - 141	100 - 197	57 - 197
OLE period				
Day 169	169	142 - 197		
Day 225	225	198 - 253		
Day 281	281	254 - 309	198 - 309	198 - 309

* Day 113 assessment for subjects continuing in OLE, the upper inclusive limit of this window is the first infusion in OLE or 42 days after last dose in double-blind period, whichever comes earlier. Assessments within 42 days after last dose in double-blind period are included for subjects discontinuing during double-blind period.

For subjects who completed Period 1 and entered Period 2 prior to the protocol revision:

Table 8.6-4: For Subjects who Completed Period 1 and Entered Period 2 prior to the Protocol Revision

Visit	Target Day	Chemistry	CBC	Total Cholesterol and Triglycerides, fasting
Double-blind (Period 1 and Period 2)				
Screening	< 1	< 1	< 1	< 1
Day 1 (Baseline)	1	1	1	1
Day 15	15	8 - 22		
Day 29	29	23 - 43	15 - 57	
Day 57	57	44 - 71		28 - 56
Day 85	85	72 - 99	58 - 99	
Day 113*	113	100 - 120	100 - 141	57 - 169
Day 128	128	121 - 134		

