Day 141	141	135 - 155		
Day 169	169	156 - 183-	142 - 197	
Day 197	197	184 - 211		
Day 225*	225	212 - 253	198 - 309	170 - 309
OLE period				

Table 8.6-4: For Subjects who Completed Period 1 and Entered Period 2 prior to the Protocol Revision

Visit	Target Day	Chemistry	CBC	Total Cholesterol and Triglycerides, fasting
Day 281	281	254 - 309		
Day 337	337	310 - 365		
Day 393	393	366 - 421	310 - 421	310 - 421

* Day 113 assessment for subjects continuing in Period 2, the upper inclusive limit of this window is the first infusion in Period 2 or 42 days after last dose in Period 1, whichever comes earlier. Day 113 assessment extends 42days after last dose in Period 1 for subjects discontinuing during Period 1. Similarly, Day 225 assessment for subjects continuing in OLE, the upper inclusive limit of this window is the first infusion in OLE or 42 days after last dose in Period 2, whichever comes earlier. Assessments within 42 days after last dose in Period 2 are included for subjects discontinuing during Period 2.

Table 8.6-5: Day Ranges for Immunogenicity Assessments at Every Scheduled Visit During the Double -Blind Period and Follow-Up Period

Visit	Target Day	Immunogenicity Day Ranges*
Double-blind period		
Day 1 (Baseline)	1	≤ 1
Day 113	113	8 - 169*
Follow-up period		
Day 56	56	1 - 70
Day 84	84	71 - 126
Day 168	168	127 - 168

* For Day 113 assessment, the upper inclusive limit of this window is the first infusion in OLE or 56 days after last dose in double-blind period, whichever comes earlier.

For subjects who completed Period 1 and entered Period 2 prior to the protocol revision:

Table 8.6-6: For Subjects who Completed Period 1 and Entered Period 2 prior to the Protocol Revision

Visit	Target Day	Immunogenicity Day Ranges*
Double-blind period		
Day 1 (Baseline)	1	≤ 1
Day 113	113	8 - 169*
Day 225	225	170 - 281
Follow-up period		
Day 56	56	1 - 70
Day 84	84	71 - 126
Day 168	168	127 - 168

*For Day 113 assessment, the upper inclusive limit of this window is the first infusion in Period 2 or 56 days after last dose in Period 1, whichever comes earlier

If a subject has more than one visit where a measurement is recorded within a window, the measurement closest to the target day will be used. In case of two visits being equidistant from the target, the later measurement will be used in the analyses. Exceptions to these rules apply to immunogenicity, where the least favorable value (toward a positive response) in the window will be used.

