For subjects who discontinue from study therapy prematurely, assessments performed after the last infusion of study drug will be included in the efficacy and safety data sets provided that these assessments are made within 42 and 56 days respectively of the last infusion.

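### The SAP's laboratory visit-window footnotes use the 42-day efficacy cut-off instead of the 56-day safety rule, so some on-treatment CBC and safety chemistry get no Day 113 visit

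*SAP*

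**What the plan says.** SAP 6.1 sets the general rule. Subjects who discontinue "will be considered on-treatment for 56 and 42 days after the last dosing in that period for safety and efficacy analysis respectively". The closing paragraph of SAP 8.6 repeats it for the efficacy and safety data sets: later assessments count "provided that these assessments are made within 42 and 56 days respectively of the last infusion". SAP 7.4.1 gives the basis for the longer figure: "The offset of 56 days is the length of 2 regular dosing cycles".

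Table 8.6-3 gives the day ranges for chemistry, CBC and fasting lipids. Its footnote, marked on the Day 113 row, has two sentences.
- For subjects continuing in the OLE, the window closes at the first OLE infusion or 42 days after the last double-blind dose, whichever is earlier.
- For subjects who stop: "Assessments within 42 days after last dose in double-blind period are included for subjects discontinuing during double-blind period".

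The footnote to the efficacy window table (Table 8.6-1) has the same wording. Table 8.6-4, for subjects who entered the former Period 2, also uses 42 days throughout. The immunogenicity window table (Table 8.6-5) instead closes its Day 113 window at the first OLE infusion or "56 days after last dose in double-blind period, whichever comes earlier".

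SAP 8.6 assigns visits by study day, not by the nominal visit on the case report form. SAP 7.6.5 summarizes laboratory changes by study day and builds shift tables at each scheduled visit.

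**The concern.** Two rules in the SAP give different answers for the same blood sample. Under 6.1 and the end of 8.6, a CBC taken 50 days after the last dose is on-treatment safety data. Under the Table 8.6-3 footnote it lies outside the Day 113 window. A sample with no derived visit cannot appear in a by-visit mean change or a shift table, and Table 9-2 lists both for the double-blind report. One programmer following 6.1 and another following the footnote would produce different safety tables.

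The gap can be reached in practice. Protocol 4.5.4.2 interrupts dosing for laboratory toxicity or adverse events, and a skipped infusion lengthens the time between the last dose and the next blood draw. The affected subjects can therefore include some whose dosing was interrupted for safety reasons.

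**Working it through.** **Inputs.**
- Double-blind infusions: "Days 1, 15, 29, 57 and 85 during Double Blind Period" (Protocol 4.5.2).
- Regular dosing interval: 28 days.
- Limits: 42 days (laboratory footnotes) and 56 days (SAP 6.1 and end of 8.6).
- Table 8.6-3 chemistry windows: Day 57 = 44–71, Day 85 = 72–99, Day 113 = 100–141.
- Table 8.6-3 CBC windows: Day 29 = 15–57, Day 85 = 58–99, Day 113 = 100–197.
- Adverse-event holds: "For all subsequent IV infusions, the dose may be delayed up to 14 days" (Protocol 4.5.4.2).

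**The plan's own figure.** 2 × 28 = 56 days, so the stated safety offset reproduces.

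**Where the disputed days fall.** For last dose on day L, the two rules differ on days L+43 to L+56, which is 14 days.

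| L | L+42 | L+56 | Disputed days | Chemistry row | CBC row |
|---|---|---|---|---|---|
| 1 | 43 | 57 | 44–57 | Day 57 | Day 29 |
| 15 | 57 | 71 | 58–71 | Day 57 | Day 85 |
| 29 | 71 | 85 | 72–85 | Day 85 | Day 85 |
| 57 | 99 | 113 | 100–113 | Day 113 | Day 113 |
| 85 | 127 | 141 | 128–141 | Day 113 | Day 113 |

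The footnote mark is on the Day 113 row only. Read that way, the last two lines are the ones affected.

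**Example 1: a subject who stops.** The last dose is on Day 57. The Day 85 dose is held for an adverse event up to the limit, 85 + 14 = Day 99, and is then skipped; the subject stops. Early-termination CBC and chemistry on Days 100–113 fall 100 − 57 = 43 to 113 − 57 = 56 days after the last dose. They are inside the 56-day safety rule and outside the footnote's 42 days.

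**Example 2: a subject who continues.** The last dose is on Day 57, only the Day 85 dose is missed, and the subject attends Day 113 and enters the OLE. One missed dose does not trigger the discontinuation rule in Protocol 3.5, which starts at two. The footnote closes the window at the earlier of the first OLE infusion (Day 113) and 57 + 42 = Day 99. The chemistry and CBC windows open at Day 100, so the Day 113 window is empty. The required Day 113 samples are 113 − 57 = 56 days after the last dose and qualify under SAP 6.1.

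**Sensitivity of Example 2 to the actual dosing day.** Samples on Day 113 are 43–56 days after the last dose when L is between 113 − 56 = 57 and 113 − 43 = 70. The ±7-day window in Protocol 4.5.2 allows L from 50 to 64.
- L = 57–64: on-treatment for safety, but lost under the footnote.
- L = 50–56: 57–63 days after the last dose, outside both limits.
- L = 71 (Day 57 plus a 14-day delay): 42 days, kept under both.

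**A fully dosed subject.** 113 − 85 = 28 days, so regular Day 113 samples are unaffected.

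**Effect of using 56 days.** Every disputed range in the table above already lies within one Table 8.6-3 chemistry window and one CBC window, so no window has to be redrawn. In Table 8.6-4 the Day 113 windows (chemistry 100–120, CBC 100–141) also contain the Days 100–113 of the Day 57 case.

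**The case against.** **The closing rule of SAP 8.6 already covers safety data for 56 days, and the footnote only says what is included.** This stands in part. The closing rule keeps the records in the safety data set, so a reader who infers that safety data are discarded goes too far. But that rule does not give a record a visit. The OLE sentence of the footnote is also an explicit upper limit, which leaves no room for later samples. SAP 7.6 refers to sponsor safety conventions that are not among the documents; they might settle the conflict, but the SAP as written does not.

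**Table 8.6-3 is not purely a safety table.** This is correct. Chemistry includes serum albumin, a secondary efficacy endpoint, and the protocol lists lipids among the supporting laboratory assessments. For these, 42 days fits the efficacy rule. That does not explain CBC, ALT, AST or creatinine.

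**The situation is rare.** This is largely correct. Protocol 5.2 asks for the Early Termination visit as soon as possible after the last dose, the Day 85 samples stay in their own row, and follow-up visits schedule no CBC or chemistry. Example 1 also depends on the last dose being on or near Day 57: after a dose on Day 64 the limit is Day 106, so samples on Days 100–106 are kept. It would be wrong to infer that every sample after a failed hold is at least 43 days from the last dose.

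**Two further inferences are not supported.**
- The chemistry upper limit of Day 141 equals 85 + 56, which might suggest that 56 days was intended. It is also the midpoint of Days 113 and 169, (113 + 169)/2 = 141. The CBC limit of 197 is likewise the midpoint of Days 113 and 281. These are ordinary midpoint windows and show nothing about intent.
- A reader might infer that the loss makes the laboratory tables look cleaner or favours abatacept. The rule is the same in both arms, and nothing in the documents indicates which way samples at 43–56 days would lie.

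**Conclusion.** The conflict is real. Both laboratory footnotes apply the efficacy limit to safety tests, against SAP 6.1 and the end of 8.6, and the SAP gives no reason for it. The consequence is narrow: certain on-treatment CBC and safety chemistry results, 43–56 days after the last dose, drop out of the Day 113 row of the by-visit change and shift tables. The clearest case is the OLE continuer who misses only the Day 85 dose, because on-schedule, protocol-required samples are lost.

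The number of subjects is probably small, and the documents give no basis for an estimate. Adverse-event and marked-abnormality summaries follow the 56-day period and do not change. The primary and secondary efficacy analyses are not affected either. The conclusion assumes that the footnote is programmed as written, applies to the Day 113 row where it is marked, and is not overridden by conventions outside the SAP.

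**What to change.** In the footnotes of Tables 8.6-3 and 8.6-4, use 56 days in place of 42 for CBC and safety chemistry. Change both kinds of sentence: those on subjects who discontinue, and those on subjects who continue into the OLE or Period 2. Keep the existing provision that the window closes at the first infusion of the next period if that comes earlier. Changing only the discontinuation sentences would leave Example 2 unresolved.

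Add one sentence stating that 42 days applies to serum albumin as an efficacy endpoint, and to lipids if they are used as efficacy measures.

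The cost is a changed number in two footnotes and one added sentence, with the matching change to the visit-window programming. No new data are needed and no printed day range has to move. The change should be made before the double-blind data are unblinded.

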Table 5.1-3: Open Label Extension								
Visit Day (± 7 days)	Day 1 (Same day as last visit of the Double Blind Period)	Day 29	Day 57	Day 85	Day 113	Day 141	Day 169 or Early Termination	Notes
Contact Central Randomization System	X	X	X	X	X	X	X	
Safety Assessments								
Adverse Event Monitoring		X	X	X	X	X	X	
████████████████████		█	█	█	█	█	█	
Targeted Physical Exam		X	X	X	X	X	X	
Weight		X	X	X	X	X	X	
Vital Signs		X	X	X	X	X	X	Seated BP, heart rate, temperature should be taken pre-dose and 60 minutes post-dose.
██████████		X	X	X	X	X	X	████████████████████
Emergency Room/Hospitalization CRF		X	X	X	X	X	X	
Laboratory Assessments								
CBC							X	
Chemistry panel			X		X		X	
Total Cholesterol and Triglycerides, fasting							X	
Urine sample for protein/creatinine ratio		X	X	X	X	X	X	To be taken from a single voided specimen. Morning collections are preferred.
eGFR							X	
Urine pregnancy test		X	X	X	X	X	X	Testing performed locally on WOCBP subjects only

Table 5.1-3: Open Label Extension								
Visit Day (± 7 days)	Day 1 (Same day as last visit of the Double Blind Period)	Day 29	Day 57	Day 85	Day 113	Day 141	Day 169 or Early Termination	Notes
Clinical Supplies								
Drug preparation by a pharmacist	X	X	X	X	X	X		
Abatacept dosing	X	X	X	X	X	X		

Table 5.1-4: Follow-Up Visits (after last dose)^a				
Visit (± 14 days)	56 Days after Last Dose	84 Days after Last Dose	168 Days after Last Dose	Notes
Adverse Event Monitoring	X	X	X	
████████████████████	■	■	■	
Targeted Physical Exam	X	X	X	
Vital Signs	X	X	X	Seated BP, heart rate, temperature
Emergency Room/Hospitalization CRF	X	X	X	
Laboratory Assessments				
Urine pregnancy test	X	X	X	Testing performed locally on WOCBP subjects only
Immunogenicity anti-abatacept Ab testing	X	X	X	
Pharmacokinetic Sampling in Blood	X	X	X	The sample will be stored until a decision is made that the testing will be needed.

^a Testing will be required only if the subject is off abatacept treatment and does not transition to commercially available treatment with abatacept.

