7.7 Other Analyses

7.7.1 Immunogenicity

Serum for anti-abatacept antibody titers are drawn at Days 1 and 113 during the double-blind period and at Day 56, 84 and 168 during the follow-up period. For this assay, for all summaries and listings unless specified otherwise, a positive relative to baseline immunogenicity response for ‘CTLA4 and possibly Ig’, ‘Ig and/or Junction Region’, respectively, is defined as:

- A missing baseline immunogenicity measurement and a positive laboratory reported immunogenicity response post-baseline.
- A negative laboratory reported baseline immunogenicity response and a positive laboratory reported immunogenicity response post-baseline.
- A positive laboratory reported baseline immunogenicity response and a positive laboratory reported immunogenicity response post-baseline that has a titer value strictly greater than the baseline titer value.

This definition will be applied for each antibody-reactivity separately.

All other ECL immunogenicity measurements will be classified as lack of positive (relative to baseline) immunogenicity response or negative immunogenicity response.

The number (and percentage) of subjects with positive samples relative to baseline will be provided. These summaries will be provided by antibody specificity, and overall. These summaries

will include frequencies by scheduled visit (including on-treatment, off-treatment and overall) and by treatment group and age group. The Day 1 measurement will be the baseline measurement for all subjects.

Immunogenicity during the follow up period will be analyzed as above and will be provided at the end of study report.

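### The follow-up Day 168 immunogenicity window ends on its target day, so on-schedule samples on days 169–182 get no visit; without the OLE, the Day 113 and follow-up Day 56 windows overlap

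*SAP*

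**What the plan says.** The immunogenicity endpoint is the proportion of subjects positive relative to baseline over time (Protocol 8.3.2.3; SAP 4.4). SAP 7.7.1 plans "frequencies by scheduled visit (including on-treatment, off-treatment and overall", and adds: "Immunogenicity during the follow up period will be analyzed as above and will be provided at the end of study report".

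Protocol Table 5.1-4 schedules three follow-up visits at 56, 84 and 168 days after the last dose, each with a 14-day tolerance either way. The last is headed "168 Days after Last Dose". Protocol Table 5.4.1-1 gives the same times in hours: 1344, 2016 and 4032.

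The SAP windows are:

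| Visit | Window | Table |
|---|---|---|
| Day 113 | 8–169, capped | 8.6-5 and 8.6-6 |
| Follow-up Day 56 | 1–70 | 8.6-5 and 8.6-6 |
| Follow-up Day 84 | 71–126 | 8.6-5 and 8.6-6 |
| Follow-up Day 168 | 127–168 | 8.6-5 and 8.6-6 |

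The Table 8.6-5 footnote caps Day 113: "the upper inclusive limit of this window is the first infusion in OLE or 56 days after last dose in double-blind period", whichever is earlier. The opening of SAP 8.6 says that the day windows do not overlap, and that visits during treatment follow the actual day rather than the visit label on the case report form. Where several immunogenicity results fall in one window, the rule is: "Exceptions to these rules apply to immunogenicity, where the least favorable value (toward a positive response) in the window will be used".

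SAP 6.1 sets a matching period boundary. The double-blind period "ends 56/42 days (for safety/efficacy analysis) after the last dose of the double-blind period or the first dosing of OLE, whichever is earlier". It also says: "Follow-up period data will be included in one of the analysis periods depending on the time of completing the study".

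**The concern.** The follow-up Day 168 window has no upper half. A sample taken one day after the target is on schedule under the protocol, yet no SAP window receives it. This is the last off-drug visit, and it is the only follow-up visit cut off in this way.

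The second problem concerns abatacept-treated subjects who stop at the end of the double-blind period, or during it, and attend follow-up without entering the OLE. Their Day 113 window stays open until 56 days after the last dose, while follow-up Day 56 opens on day 1. The printed ranges therefore do not deliver the exclusivity that SAP 8.6 states, and no sentence says which visit takes a sample that fits both. Because a positive displaces a negative within a window, a result first seen at follow-up can be reported as a Day 113 result. The Day 113 row would then mix end-of-treatment status with status some weeks later.

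**Working it through.** **Inputs.** Follow-up targets of 56, 84 and 168 days after the last dose, ±14 days (Protocol Table 5.1-4). Windows and the Day 113 cap (SAP Tables 8.6-5 and 8.6-6). Last scheduled double-blind dose on Day 85 (Protocol 4.5.2).

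**Origin of the follow-up days.** The SAP tables do not state one. The protocol hours divided by 24 give 1344/24 = 56, 2016/24 = 84 and 4032/24 = 168 days after the last dose, so I use that origin.

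**Coverage of each visit by its own window.** Permitted days = target − 14 to target + 14, which is 29 days.

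| Visit | Permitted | Own window | Days inside |
|---|---|---|---|
| Follow-up Day 56 | 42–70 | 1–70 | 29 of 29 |
| Follow-up Day 84 | 70–98 | 71–126 | 28 of 29 (day 70 goes to Day 56) |
| Follow-up Day 168 | 154–182 | 127–168 | 168 − 154 + 1 = 15 of 29 |

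For Day 168 the uncovered days are 169–182: 182 − 169 + 1 = 14 of 29. The inner bounds are midpoints between targets, (56 + 84)/2 = 70 and (84 + 168)/2 = 126, but the last upper bound is the target itself. If the last dose were counted as day 1, the permitted days would be 155–183 and the gap 169–183. The gap moves but does not close.

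**Overlap in Table 8.6-5, last dose Day 85, no OLE.**

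- Day 113 window ends at min(169, 85 + 56) = study Day 141.
- Follow-up Day 56 window: 85 + 1 = 86 to 85 + 70 = 155.
- Shared study days: 86–141, which is 56 days.
- An on-time Day 113 sample is 113 − 85 = 28 days after the last dose, so it is inside the shared range.
- An on-target follow-up Day 56 sample is on study Day 85 + 56 = 141, also inside.
- Of the 29 permitted days for follow-up Day 56, days 42–56 (15) lie in both windows and days 57–70 (14) lie only in follow-up.

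The 15/14 split is the same for last doses on Days 1, 15, 29 and 57. The overlap itself is 56 days in each case except Day 1, where it is 50 because the Day 113 window opens on study Day 8.

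**Who is not affected by the overlap.** For OLE entrants the Day 113 window closes at the first OLE infusion and follow-up runs from a later last dose. Placebo subjects who never receive abatacept are outside the immunogenicity population (SAP 6.3.4).

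**Would a fixed day cut do?** For a Day 85 last dose it would have to fall between day 28 (the Day 113 sample) and day 42 (the earliest permitted follow-up sample). Protocol 4.5.4.2 allows a dose to be skipped. If Day 85 is skipped, the last dose is Day 57 and the Day 113 sample is 113 − 57 = 56 days after it. Such a cut would then misplace the Day 113 sample.

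**The case against.** The bound of 168 is not arbitrary: Protocol 3.1.4 describes a 168-day follow-up period, and the SAP may simply have copied it. That may explain the number, but it does not reconcile it with the ±14-day tolerance.

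On the overlap the other side is stronger. SAP 8.6 states that its windows do not overlap, and SAP 6.1 puts follow-up data in a single analysis period, so counting one sample at two visits is plainly not intended. The 56-day limit is a deliberate safety convention. It appears in SAP 6.1, in the Table 8.6-5 footnote and at the end of SAP 8.6 for early discontinuers, and SAP 7.4.1 justifies it as two dosing cycles and about four half-lives. The least-favorable rule is openly conservative. SAP 7.7.1 also plans on-treatment and off-treatment summaries, so the by-visit row is not the only evidence on timing.

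All of that stands, and it narrows the point. What remains is that the printed ranges do not achieve the stated exclusivity. If the SAP 6.1 period is assigned first, double counting stops, but follow-up Day 56 samples taken on or before target are pooled into Day 113.

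A reader might infer that the table could not then show when antibodies appeared. The planned on- and off-treatment summaries do not support so strong a statement.

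**Conclusion.** Minor, but wrong as written for follow-up Day 168: 14 of 29 permitted days have no analysis visit in either table. The overlap in Table 8.6-5 needs clarification. It touches 15 of the 29 permitted days for follow-up Day 56, and only for abatacept-treated subjects who skip the OLE and attend follow-up, which excludes those moving to commercial abatacept (Protocol Table 5.1-4, footnote a).

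These are counts of calendar days, not shares of subjects. The documents do not forecast how many subjects skip the OLE or are sampled on those days, so no change in a positivity rate is claimed. The counts assume that follow-up days run from the last dose, as in the protocol. The primary endpoint, the other efficacy analyses and the sample size are untouched.

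Two stronger readings are not supported:

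- A reader might infer that late Day 168 samples vanish from the analysis. They lose a scheduled-visit assignment; the overall or off-treatment counts may still include them.
- A reader might extend the overlap to Day 225 in Table 8.6-6 (window 170–281), which has no last-dose cap. No effect is demonstrated. The Period 2 schedule is not in the current protocol, and Period 2 data are only listed, apart from end-of-study safety summaries on the cumulative abatacept period. For abatacept-first subjects without the OLE, that period "starts with the first dosing of Period 1 and ends 56 days after the last dosing of Period 1".

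**What to change.** 1. In Tables 8.6-5 and 8.6-6, end the follow-up Day 168 window at day 182 or later, and state that follow-up days count from the last dose. Extending the window symmetrically about its target would give 168 + (168 − 126) = 210.
2. In Table 8.6-5, state that each immunogenicity sample belongs to one analysis visit. Where the Day 113 and follow-up Day 56 windows both apply, the scheduled visit (Day 113/Early Termination or follow-up) decides, before the least-favorable rule is applied. The actual-day convention in SAP 8.6 is worded for visits during treatment, so using the scheduled visit for post-treatment samples need not conflict with it.

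The cost is one bound in two tables, one origin statement and one assignment rule. No extra samples are needed.
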